## 3.0 Introduction

Psoriasis is an autoimmune illness characterized by chronic non-contagious skin manifestations  $^{1}$  caused by an immunologically accelerated cell turnover  $^{2}$ . The result is an abnormal accumulation of cells to the skin surface  $^{2}$  causing inflammation, thickening, scaling, pruritic changes and pain that could extend to the surrounding joints  $^{3}$ .

There are five types of psoriasis depending on the symptoms and severity. The most common type of psoriasis (approximately 80%) is "plaque psoriasis" where raised and inflamed red lesions covered by silver-white scales develop.

The causes of psoriasis are somewhat unknown; however it is believed that genetics and the immune system are involved. It is postulated that 10% of the population has a gene that predisposes them to psoriasis; however, only 2% of the worldwide population develops the illness. The currently held belief is that a multifactorial genetic predisposition and an environmental trigger are required for the disease to manifest. Potential triggers include stress, an injury to the skin and certain medications such as lithium, antimalarials, Inderal, quinidine and indomethacin. Injury induced psoriasis is known as the Koebner phenomenon. There are certain triggers that could cause specific types of psoriasis. For instance, upper respiratory infections, streptococcal throat infections, tonsillitis, beta-blockers as well as the three triggers mentioned above can cause guttate psoriasis. Appreciation of the different types of Psoriasis and related environmental triggers becomes important in studying regional variations in the epidemiology and risk factors of the disease.

On the cellular level, the causes of psoriasis begin with T-cells, which have been shown to be involved in the development of psoriasis, more specifically Th1 and Th17 cells. When the cytokine IL-12 is produced, Th1 cells differentiate which subsequently secrete TNF- $\alpha$  and IFN- $\alpha$ . These two cytokines cause vasodilatation, leukocyte migration, activation of keratinocytes and, later on, the activation of dendritic cells. The latter effect will begin a

cycle of inflammation. Th17 cells are also involved. After they are activated by  $\underline{\text{IL}}$ -1,  $\underline{\text{IL}}$ -6 and  $\underline{\text{TGF-}\alpha}$ , they produce  $\underline{\text{IL}}$ -17 and  $\underline{\text{IL}}$ -22 which also stimulate keratinocyte activation and proliferation. Clearly, the overstimulation of the keratinocytes is the main cause of the acceleration of the skin cell growth cycle mentioned earlier. Understanding of the underlying disease process is essential in defining treatment targets.

Psoriasis affects approximately 125 million people worldwide, which consist of 2-3% of the total population. In Canada it is estimated that more than 1 million individuals, have psoriasis. The prevalence of the disease is 0.8-1%. However, these statistics vary according to race, ethnic background, region, age and gender

Psoriasis has a major impact on the patient's quality of life with approximately 60% of the patients considering the illness to greatly impact their life. However, in Canada, according to a study by Lynde et al., 35% of the patients with psoriasis considered the disease to be a substantial problem in their daily life. In the same study, 54% of patients had lesions on more than 3% of their body. Furthermore, psoriasis has a greater negative impact in women and younger patients. Although not typically considered a severe or life threatening condition, in its severe form, affecting more than 10% of the body, life expectancy may be decreased for as much as 50% when comparing mild to severe psoriasis 6, 10

The typical first line of treatment for early mild psoriasis is topical medications. These include creams, ointments and shampoos that slow down or normalize the accelerated growth cycle of the skin cells and hence reduce the inflammation. Corticosteroid ointments are generally the first line topical treatment of choice and are effective in reducing the swelling and the redness of the lesions. Corticosteroids provide symptomatic relief but may not cure the disease and may even cause exacerbation with high dose or prolonged use. Topical corticosteroids are associated with possible side effects resulting in skin damage, such as skin thinning, changes in pigmentation, easy bruising, stretch marks, redness and dilated blood vessels on the surface. Furthermore, if

applied on, in or near the eye, cataracts and glaucoma may occur.  $\frac{13}{12}$ 

There are some topical drugs that do not contain corticosteroids, like Dovonex (calcipotriene), and Vertical (calcitriol). Dovonex and Taclonex (calcipotriene and betamethasone dipropionate) have some non-severe side effects, the most common being skin irritation, stinging and burning for Dovonex and itching, rash, skin thinning and burning for Taclonex. Furthermore, the patient has an increased risk of skin tumors because of the sensitivity to light. Some antipsoriatic topical drugs contain retinoids, such as Tazorac (tazarotene). These medications act less rapidly than corticosteroids, but have fewer adverse effects. Other topical medications for psoriasis include Zithranol-RR (Anthralin), vitamin D3 or A, coal tar and salicylic acid. Anthralin has no long-term side effects, though it may cause skin irritation and may stain light-colored hair and unaffected skin. 14

For moderate or severe psoriasis, affecting more than 3% of the body surface area, topical treatments are generally not effective and more aggressive therapy is required. Phototherapy is an effective second line treatment for moderate psoriasis or mild disease that has not responded to topical therapy. Phototherapy consists of regularly exposing the skin to ultraviolet (UV) light which reduces inflammation by reducing T-cell proliferation. Ultraviolet light treatment is classified as UVA and UVB. UVA light is the principle component of sunlight and it is used in combination with photosensitizing medications such as psoralen when it is referred to as PUVA. The disadvantages of UVA and PUVA treatments include a high risk of cancer along with immediate reactions including, nausea, headache, burning of the skin and photosensitivity. Use of topical PUVA or baths have been proven to be a safer and effective alternative. 22-23

UVB treatment is based on another component of sunlight and it is available as broadband or narrowband therapy. Broad band UVB phototherapy uses light with a wavelength range between 290 and 350 nanometers. UVB treatment is less carcinogenic when compared to UVA and does not require co administration of medications. However, it may be less

effective. Narrowband UVB uses light in the 311-313 nanometer wavelength range. It is highly effective and does not require the use of photosensitizing medications. 22-23

Compliance with treatment is essential for success of phototherapy. This treatment is most recommended when the patient has plaque psoriasis, guttate psoriasis or psoriasis on the palms and soles. However, if employed over a long period of time, it is associated with an increase of risk of skin cancers. Recently two new phototherapy treatments have been by the FDA for mild to moderate psoriasis: the excimer and pulsed dye laser which better control the beam of light (UVB) to specifically target the affected skin area. 4.15

For moderate to severe psoriasis that does not respond to topical agents or phototherapy, systemic treatments are used. These include traditional and biologic disease modifying agents. Methotrexate and cyclosporine are traditional systemic disease modifying agents that have been proven to be efficacious in the management of psoriasis. Cyclosporine binds to dihydrofolate reductase leading to the inhibition of synthesis of DNA, RNA, thymidylates and proteins and thus reducing the skin proliferation. Adverse effects associated with methotrexate include liver damage reduced leukocytes, infections and malignancies.

Cyclosporine suppresses the immune system and prevents skin cell proliferation. While efficacious in controlling the symptoms of psoriasis, cyclosporine has an increased risk for serious adverse events and prolonged use or use by patients with chronic conditions or compromised immune systems is not recommended. Among the side effects of cyclosporine the most important are decreased kidney function, headache, hypertension, elevated cholesterol, excessive hair growth, tingling or burning sensation in arms and/or legs, skin sensitivity, increased growth of gum tissues, influenza-like symptoms, upset stomach, tiredness and muscle, bone or joint pain. Also, if the drug is taken over a long period of time, the patient could develop skin cancer or kidney damage. This risk increases with a longer exposure. 

Biologic systemic agents and specifically anti-TNF- $\alpha$  inhibitors have been developed in recent years and have been proven efficacious in the management of patients. As mentioned earlier, TNF- $\alpha$ , a cytokine, causes the proliferation of keratinocytes through the mediation of inflammatory Th1 cells (CD4 T-cells) that bind to MHC (major histocompatility complex) class II molecules and present an antigen to the T-cells. Some of these cytokines, including TNF- $\alpha$ , stimulate the activation of macrophages which cause inflammation and induce vascular permeability, leukocyte migration and the formation of new vessel networks. TNF is over expressed in psoriatic plaques and TNF-induced proteins are found in psoriatic lesions but not in healthy areas. This would suggest that TNF is involved in the pathogenesis of the disease by increasing the inflammatory process and augmenting the proliferation of keratinocytes in the affected regions. It is also postulated that TNF increases cellular adhesion, activation and promotion of angiogenesis. Therefore, agents that block the activity of TNF- $\alpha$  have been proven to treat psoriasis and reduce inflammation. 

Adalimumab (Humira®) is a fully human anti-TNF- $\alpha$  monoclonal antibody that is an analogue to human IgG1. It attaches to TNF and prevents its binding to p55 and p75 TNF receptors on the cell surface. It is currently approved for the treatment of psoriasis, juvenile and adult rheumatoid arthritis, ankylosing spondylitis, psoriatic arthritis and Crohn's disease. Currently dosing in patients with moderate to severe psoriasis involves an initial dose of 80mg subcutaneously, followed by a 40mg injection every second week beginning one week after the initial 80mg dose.

Due to their immune suppression properties, anti-TNF alpha agents including adalimumab may be associated with increased risk for serious infections including tuberculosis, candidiasis, listeriosis, pneumocystis, pneumonia, pyelonephritis, septic arthritis and septicemia. Patients may also be at risk for serious opportunistic infections. However, these events have been predominantly reported in patients with compromised immune systems. Some non-severe adverse effects are a moderately painful injection

site including redness, itching, bruising, pain or swelling, stomach pain, nausea, headache and back pain. Rare side effects include malignancies, reversible lupus (without renal or CNS complications) and cytopenias. Therefore all patients treated with anti-TNF alpha agents must be monitored for serious infections and particularly tuberculosis before, during and after treatment. In addition monitoring of liver function, CBC and hepatitis profile are recommended.

The efficacy of adalimumab in controlling the symptoms of psoriasis has been demonstrated in several controlled clinical trials. Taken collectively the results of these studies that have been conducted on over 1600 patients with moderate to severe chronic plaque psoriasis who were candidates for systemic therapy or phototherapy have shown that adalimumab is efficacious in controlling the symptoms of psoriasis and in improving the quality of life of patients. More specifically, when compared to placebo or methotrexate, patients treated with adalimumab had a significantly higher therapeutic response rate, defined as achieving a PASI 75 and a Physician Global Assessment (PGA) value of  $\leq 1$  (indicating clear or minimal disease) at 16 weeks. The magnitude of effect versus placebo ranges from four-fold (79.6% versus 18.9%) to ten-fold (70.9% versus 6.5%) for PASI 75 and from 2.5 times (73.1% versus 30%) to 14.5 times (62.2% versus 4.3%) for PGA of clear or minimal. When compared to methotrexate the magnitude of effect is 2.2 times for PASI 75 (79.6% versus 35.5%) and 2.5 times for PGA of "clear or minimal" (73.1% versus 30%) 1.11-18,22-29. In addition, in one clinical trial patients crossed over to placebo after 33 weeks of treatment with adalimumab were significantly more likely to lose therapeutic response when compared to patients that were maintained on adalimumab up to week 52. With respect to quality of life, when compared to patients treated with placebo or methotrexate those treated with adalimumab in these controlled clinical trials have had better improvement in the Dermatology Quality of Life Index (DLQI) total score as well as in the disease severity, pain and pruritus subscales. Better improvement in the Physical and Mental subscales of the Medical Outcomes Study Short Form 12 (SF-12) was also observed for the adalimumab treated patients when compared

to placebo.

In Canada, the Canadian Expert Drug Advisory Committee (CEDAC) of the Canadian Agency for Drugs and Technologies in Health has recommended adalimumab in the treatment of psoriasis under the following conditions:

- i. Patient is diagnosed with severe debilitating psoriasis; and
- ii. Body surface involvement of more than 10% and / or significant involvement of the face, hands, feet or genital areas; and
- iii. Failure to respond to, contraindication or intolerance to methotrexate and cyclosporine; and
- iv. Failure to respond to, intolerant to or unable to access phototherapy.

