of illness. The design is that of a prospective observational study with its inherent biases including confounding by indication. Statistical methods including multi-variate models and propensity scores will be used to adjust between group differences with respect to prognostic baseline characteristics. Mixed effects models will be incorporated to compensate for unequal follow up and lack of precisely scheduled visits. The design and statistical analysis employed are therefore required and appropriate to produce a valid real – life assessment and comparison of the different modes for the management of psoriasis that are currently used in Canada.

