#### months.

- iv. Change in Body Surface Area (BSA) of psoriasis involvement at 6, 12, 18 and 24 months. The BSA is an indicator of disease severity and the affected area is expressed as a percentage of the total body surface area.
- v. Change in Patient Global Assessment of Disease Activity based on a six point Likert Scale at 3, 6, 12, 18 and 24 months.
- vi. Change in the Dermatology Quality of Life Index (DLQI) at 3, 6, 12, 18 and 24 months. The DLQI is a self administered questionnaire comprised of 10 items assessing a patient's skin and problems associated with skin disease. The 10 questions in the DLQI converge into six domains that measure symptoms and feelings, daily activities, leisure, work and / or school, personal relationships and satisfaction with treatment.
  - i. Proportion of patients achieving and time to  $\underline{DLQI} \le 1$  through the 24 months of treatment.
- vii. Change in Beck Depression Inventory at 6, 12 and 24 months: This will be used to assess the presence and severity of depression. It consists of 21 items converging to two scales measuring somatic and affective components of depression. The questions assess hopelessness and irritability, cognition such as guilt or feelings of being punished, as well as physical symptoms such as fatigue, weight loss and loss of interest in sex. Given the important emotional and social impact of psoriasis assessing psychological impairment is important in order to fully appreciate the impact of the disease and effect of treatment on the patient's life.
- viii. Change in Medical Outcomes Study Short Form 12 (SF-12) at 6, 12 and 24 months. The SF-12 Health is a 12-item general health self administered

- questionnaire consisting of 8 scales measuring Physical Function, Physical Role limitations, Vitality, General Health, Pain, Social Function, Emotional Role limitations, and Mental Health.

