## 6.1 Selection of Study Population

Patients will be enrolled from the offices of community dermatologists across Canada treating patients with Psoriasis. The sample of physicians invited to participate in the study will be selected in a way that it is a random representative sample of the Canadian population and distribution of dermatologists.

All patients with psoriasis treated at the participating centers will be potentially eligible

to be included in the study. Those fulfilling the study inclusion and exclusion criteria will be invited to participate in the study by the site investigator or designee. Treatment will be according to the treating physician's judgment and routine care and must adhere to the product monograph and regional regulatory requirements. Use of medications for the management of psoriasis that is off—label or not in accordance with existing regulations will not be permitted. Prior to inclusion in the study all patients will be required to sign a written informed consent agreeing to allow use of their data in the study. Since this is not an interventional study and patients are treated as per routine care the purpose of the informed consent will be to allow the use of the data and contact of the patients by the study personnel as required. The study protocol, informed consent, questionnaires and participating physicians will be approved by a central or local independent ethics review board as required by regional or institutional regulations.

Changing the patient's treatment including initiation of treatment with adalimumab must be exclusively the treating physician's decision and must be reached prior to patient screening and enrollment and has to be entirely independent of the conduct of the study. The observational nature of the study dictates that all treatments used in the current study, including adalimumab, must be prescribed as per routine care and in accordance to the Canadian and provincial marketing authorization and criteria.

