| Dose                                                      | X     |    |    |    |    |    |
| Duration                                                  |       |    |    |    |    |    |
| Reason for discontinuation                                |       |    |    |    |    |    |
| Concomitant Medications (Emphasis on Psoriasis Treatment) | X     | X  | X  | X  | X  | X  |
| Concomitant Psoriatic Arthritis                           | X2    |    |    |    |    |    |
| Rheumatoid Factor                                         | X2    |    |    |    |    |    |
| C - Reactive Protein or hs- CRP                    | X2    | X2 | X2 | X2 | X2 | X2 |
| Erythrocyte Sedimentation Rate (ESR)                      | X2    | X2 | X2 | X2 | X2 | X2 |
| Clinical Laboratory Tests                                 | X2    | X2 | X2 | X2 | X2 | X2 |

|                                                                    | Month |    |    |    |    |    |
|--------------------------------------------------------------------|-------|----|----|----|----|----|
| Variable                                                           | 0     | 3  | 6  | 12 | 18 | 24 |
| Visit Number                                                       | 1     | 2  | 3  | 4  | 5  | 6  |
| Body Surface Area (BSA)                                            | X     |    | X  | X  | X  | X  |
| Psoriasis and Arthritis Screening Questionnaire (PASQ)             | X     | X  | X  | X  | X  | X  |
| Use of Phototherapy                                                | X     | X  | X  | X  | X  | X  |
| Physician's Global Assessment of Disease Activity (6 Point Likert) | X     | X  | X  | X  | X  | X  |
| Patient's Global Assessment of Disease Activity (VAS)              | X3    | X3 | X3 | X3 | X3 | X3 |
| Dermatology Life Quality Index                                     | X3    | X3 | X3 | X3 | X3 | X3 |
| Medical Outcomes Study – Short Form 12                             | X3    |    | X3 | X3 |    | X3 |
| Health Care Utilization Questionnaire                              | X3    |    | X3 | X3 |    | X3 |
| Beck Depression Inventory                                          | X3    |    | X3 | X3 |    | X3 |
| Work Limitations Questionnaire                                     |       |    | X3 | X3 |    | X3 |
| Rheumatology Consult4                                              | X     | X  | X  | X  | X  | X  |

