#### Physical Examination and Medical History:

During the baseline assessment the results of a complete physical examination and medical history will be recorded in the study Case Report Form. For subsequent follow up assessments, only clinically important changes in the Medical History and Physical Examination will be recorded.

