# 6.5.2 Product Supply:

In the current study patients will be treated with topical agents, traditional systemic agents and adalimumab as monotherapy or in combination. As an observational study all treatments will be accessed as per routine customary practice in the region. More specifically, AbbVieE will not supply or reimburse for any treatment used by the patients in the study. Patients will be prescribed the medications by the treating physician and will acquire these through the available insurance plan / government reimbursement or purchase with their own funds. All medications will be used in accordance to the current marketing label, the product monograph and regional requirements.

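### Face, hand, foot and genital involvement is half of an adalimumab condition cited in the protocol but is not a listed baseline item, so the planned adjustment can reach it only through proxies

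*Protocol*

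**What the plan says.** Protocol 3.0 (repeated in SAP 2.1) reports that a Canadian advisory committee "has recommended adalimumab in the treatment of psoriasis under the following conditions". There are four conditions, all to be met: severe debilitating disease; the extent-or-site condition; failure of, or unsuitability for, methotrexate and cyclosporine; and failure of, intolerance to or no access to phototherapy. The second condition is an either/or: "Body surface involvement of more than 10% and / or significant involvement of the face, hands, feet or genital areas".

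Protocol 6.1 (SAP 2.9) says that all treatments "must be prescribed as per routine care and in accordance to the Canadian and provincial marketing authorization and criteria". Protocol 6.5.2 says that patients "will acquire these through the available insurance plan / government reimbursement or purchase with their own funds".

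For extent of disease, Protocol 5.3.2 defines BSA so that "the affected area is expressed as a percentage of the total body surface area". Table 1 (Protocol 6.5, SAP 2.6) schedules BSA at months 0, 6, 12, 18 and 24. No row in either table names a body site, and no title in the SAP list of tables does so. Protocol 6.5.1 adds that at baseline "the results of a complete physical examination and medical history will be recorded in the study Case Report Form", without mentioning lesion location.

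Protocol 4.0 acknowledges confounding by indication and answers it with multivariable models and propensity scores: "propensity scores will be used to adjust between group differences with respect to prognostic baseline characteristics". SAP 3.8 takes as potential confounders the baseline variables with P<0.15 or a more than two-fold difference between groups. SAP 3.10 applies the adjustment to PGA 0/1 at six months.

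**The concern.** Treatment is chosen by the physician, so the primary comparison depends on measuring the reasons for that choice. Here the protocol itself names one possible reason, and the listed data do not include it. A variable that is not recorded cannot be screened at P<0.15, enter a propensity score or define a stratum.

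BSA cannot stand in for site. Because the condition is an either/or, a patient with BSA of 10% or less meets it only through special-site disease. Eligibility has no BSA minimum (Protocol 6.1.1, SAP 2.8.1), so such patients can enroll. To the extent that the condition guides prescribing, low-BSA adalimumab patients will more often have face, hand, foot or genital disease than low-BSA comparator patients. If that disease responds differently on the PGA, the adjusted month-6 contrast mixes a site effect with the treatment effect. The DLQI, BDI and WLQ contrasts would be exposed in the same way if site affects those outcomes.

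**Working it through.** The plan states no figure on this point, so there is none to reproduce. The check is textual, followed by an illustration of possible size.

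**Text.** The access condition has two alternatives. The first, BSA above 10%, is measured. The second, special-site disease, has no row in either Table 1. Protocol 9.0 restricts collection to data specified in the protocol, so the gap will not close by itself.

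**Inputs from the documents.** Protocol 10.3 plans for 50% response on adalimumab and 40% on traditional systemic agents: 0.50/0.40 = 1.25, the inverse of its stated RR of 0.80.

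**Assumed inputs (not in the documents).** Special-site disease in 35% of patients, independent of BSA; BSA above 10% in 40% or 60%; adalimumab started by 60% of those meeting the either/or condition and by a fraction e = 5% or 20% of the rest; comparator response 40%, multiplied by 0.9 if BSA is high and by k if special sites are involved; true RR 1.25 in every cell.

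**Step 1: special-site prevalence at BSA of 10% or less.**
- Adalimumab: p1 = 0.35×0.60 / (0.35×0.60 + 0.65×e). This is 0.210/0.2425 = 87% at e = 5%, and 0.210/0.340 = 62% at e = 20%.
- Comparator: p0 = 0.35×0.40 / (0.35×0.40 + 0.65×(1−e)). This is 0.140/0.7575 = 18% (0.185) and 0.140/0.660 = 21%.
- At BSA above 10% both groups have 35%.

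**Step 2: observed RR in the low-BSA stratum** = 1.25 × [1 + p1(k−1)] / [1 + p0(k−1)]. For k = 0.6 and e = 5%: 1.25 × 0.654/0.926 = 0.88.

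**Step 3: RR standardised over BSA to the whole population.** For k = 0.6, e = 5% and 40% with high BSA, responses are 0.327 v 0.370 (low BSA) and 0.387 v 0.310 (high BSA). So (0.6×0.327 + 0.4×0.387) / (0.6×0.370 + 0.4×0.310) = 0.351/0.346 = 1.01.

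| Assumed k | Low-BSA RR | BSA-adjusted RR (true 1.25) |
|---|---|---|
| 0.6 | 0.88–1.03 | 1.01–1.15 |
| 0.75 | 1.03–1.12 | 1.11–1.19 |
| 1.0 (not prognostic) | 1.25 | 1.25 |
| 1.2 | 1.35–1.41 | 1.29–1.35 |

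**Step 4: a second set of assumptions.** BSA above 10% in 40% or 60%; special-site disease in 30% or 50%; the rule binding 50% or 100% of patients; half of those with access starting adalimumab; k = 0.6 or 0.8; no effect of BSA on response. Over the 16 combinations, special-site prevalence at low BSA is 46–100% (adalimumab) against 18–40% (comparator). The BSA-adjusted RR is 1.08–1.23 when standardised to the adalimumab patients and 0.98–1.22 when standardised to the whole population.

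In the first model, stratifying on site as well as BSA returns 1.25 in every scenario, by construction. These are risk ratios against a pooled comparator with BSA as the only adjuster. The plan fits logistic models to three groups with more covariates, so the figures show what is possible and are not a forecast.

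**The case against.** Much of the opposing case stands.

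- *The condition is a recommendation.* A reader might infer that adalimumab funding turns on special-site disease. The documents do not say so. Protocol 3.0 reports advice, Protocol 6.1 does not equate provincial criteria with it, the approved indication in Protocol 4.0 has no site condition, and private insurance and own funds are allowed. How many patients the condition touches is unknown.
- *The plan does not adjust for BSA alone.* Any recorded baseline characteristic that passes the screen can enter, including PGA, DLQI, prior treatment and phototherapy. The other three conditions are at least partly captured this way, and these variables may partly act as proxies for site. None records location.
- *Adjusting for BSA is not shown to do harm.* A reader might infer that conditioning on BSA creates the bias or makes it worse. The imbalance exists before any conditioning: with 40% high BSA and e = 5%, the site-treatment odds ratio is about 4 overall, against (0.60/0.40)/(0.05/0.95) = 28.5 within low BSA. Low BSA concentrates the imbalance and does not create it. In the 16 scenarios of Step 4, BSA adjustment is closer to the truth than the crude RR in all 16 when standardised to adalimumab patients. Standardised to the whole population it is closer in none if BSA has no effect on response, but in 11, 15 and 16 of 16 if high BSA multiplies response by 0.9, 0.8 or 0.7.
- *Site may be captured anyway.* The baseline physical examination could hold it, and neither the CRF nor the bodies of the mock tables were available. The point is therefore that site is not a listed, structured item. It cannot be said that no visit records it.
- *Site may not be prognostic for PGA 0/1.* The documents are silent. If it is not, there is no bias in the primary contrast from this source.

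What remains is that the protocol names this variable as a possible driver of treatment and the plan gives the analyst no defined way to use it.

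**Conclusion.** The omission is clear in the text: neither Table 1 lists special-site involvement, and whole-body BSA cannot replace it. Residual confounding of the adjusted month-6 PGA contrast follows only if two further things hold: the condition influences prescribing among enrolled patients, and special-site disease predicts PGA 0/1 beyond what the recorded variables carry. The documents establish neither, so both size and direction are unknown. Illustrative BSA-adjusted RRs run from about 1.0 to 1.35 against a true 1.25, depending on the assumptions and the standardisation, and equal 1.25 if special sites are not prognostic. At the unfavourable end, the whole of the plan's minimum important effect would be hidden. This is a cheap improvement to a study that already acknowledges confounding by indication. It is not a demonstrated bias in a known direction.

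**What to change.** Add to the month-0 column of both Table 1s and to the baseline CRF: *significant psoriasis of the face, of the hands, of the feet, of the genital area (yes/no for each)*. For patients already enrolled, retrieve it from the chart where recorded; Protocol 6.5.1 already accepts chart review as a baseline source.

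State in SAP 3.2 and 3.8 that special-site involvement enters the propensity score and the adjusted models regardless of the P<0.15 screen, with a BSA-by-site term, because the condition is an either/or. Where the item cannot be recovered, report a quantitative bias analysis over stated ranges of prevalence and prognostic effect.

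Payer for the new treatment may be recorded for description or a sensitivity analysis. It should not be forced into the propensity score: it may act mainly as an instrument, predicting treatment with little direct bearing on outcome.

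The cost is a few tick-boxes for a physician who already scores BSA and PGA, a short addition to the SAP, and some chart review. No treatment decision changes.
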